4.3 Exclusion criteria

1) CT scan and irregular lobulated hematoma, such as intraventricular hemorrhage (because no accurate measurement of bleeding);

2) Severe liver disease or impaired liver function;

3) Pregnant or lactating women;

4) The usage of anticoagulation or antiplatelet aggregation drug history (including cilostazol, aspirin, dipyridamole, heparin, low molecular weight heparin, hirudin, dabigatran, rivaroxabanand warfarin);

5) Non informed consent.

4.4 Rejection standard

1) The subjects failed to meet the inclusion criteria and were mistakenly included in the trial.

2) The subjects met either of the exclusion criteria.

3) No record of any further visits.

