4.2 Inclusion criteria

1) Patients with spontaneous intracerebral hemorrhage (enhanced by cerebral arterial CT or cerebral angiography confirmed rupture of non aneurysm or arteriovenous malformation);

3) Age 18-65 years, male or not pregnant female;

4) GCS score at admission;

5) Head CT or MRI examination confirmed cerebral hemorrhage at super tentorium of cerebellum and the amount of bleeding in 10ml-45ml (Duotian formula to calculate the hemorrhage volume);

6)During the hospitalization, no urokinase and other hemostatic drugs were used except for the use of K1 and vitamin D in the project;

7) Informed consent form signed by the patient's family.

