4.5 Exit test standard

4.5.1 The researchers decided to quit

1)During the clinical trial, the subjects experienced other complications, complications,

or special physiological changes, and were not allowed to continue the experiment..

2) Serious adverse events and important adverse events, it is not appropriate to continue to accept the test.

3) The subjects had poor compliance.

4) The test process meets the rejection criteria.

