4.5.3 Withdrawal case management

In the case of the withdrawal from the trial, the researchers should actively take measures to complete the final examination as soon as possible to analyze the efficacy and safety. All trial cases should be completed in the case report form and the reasons for the withdrawal.

5 Suspension test standard

The discontinuation test means that the clinical trials have not been completed by the end of the program. The purpose of the suspension test is to protect the rights and interests of the subjects, to ensure the quality of the test and to avoid unnecessary economic losses. Standard for discontinuation of a test:

1) serious safety problems in the test, should promptly stop the test.

2) The trial found that the drug did not have clinical value and should discontinue trials, on the one hand, to avoid delaying the effective treatment of the subjects while avoiding unnecessary economic losses.

3) In the experiment, it was found that the clinical trial program had major errors and

it was difficult to evaluate the effect of the drug; or a well-designed design, which made important deviations in the implementation, and continued, it is difficult to evaluate the effect of the drug.

4) The applicant asked for a suspension (such as funding reasons, management reasons, etc.).

6 Treatment Plans

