7.5.3 Medication and treatment are permitted

(1) The other combined diseases without affecting the curative effect and safety evaluation, can be symptomatic medication, but it must be the case report form to record the medicine general or other treatment, dosage, reason, use frequency and time etc, so as to summarize, analyze and report.

⁽²⁾The follow-up period can use cognitive rehabilitation methods, including occupational therapy, implicit memory rehabilitation, errorless learning, cognitive neuropsychological rehabilitation, rehabilitation and computer assisted cognitive rehabilitation, virtual remote control via the Internet, and the electromagnetic stimulation, should be recorded in detail in CRF.

⁽³⁾The combination drugs used for adverse events during the trial should be recorded in CRF.

8 Therapeutic evaluation standard

Main outcome measures: the amount of intracerebral hemorrhage (0d, 1D, 3D, 7D) at each time after the onset of disease.

Main outcome measures: (1) the amount of the time changes in blood coagulation, platelet levels and GCS scores after the onset (0d, 1D, 3D, 7D); (2) days in ICU; (3) the total hospitalization days; (4) complications including neurological complications, complications, blood coagulation circulatory complications after cerebral hemorrhage; (5) 1m and 6m mRS score.

9 Safety evaluation

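### Rejection item 4.4(2) has no time limit, so a patient whose bleed enters the ventricle or turns irregular after randomisation can be rejected for a form of the outcome

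*Protocol*

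**What the plan says.** Protocol 4.4 lists three grounds for rejection. Item 1 is confined to enrolment errors: "The subjects failed to meet the inclusion criteria and were mistakenly included in the trial". Item 2 is not: "The subjects met either of the exclusion criteria". Item 3 concerns patients with no further visit records.

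Protocol 4.5.1, on exits decided by the researchers, adds as item 4: "The test process meets the rejection criteria".

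The first exclusion criterion in 4.3 is "CT scan and irregular lobulated hematoma, such as intraventricular hemorrhage (because no accurate measurement of bleeding"). Its stated reason is measurement.

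Protocol section 8 gives as the first-listed main outcome "the amount of intracerebral hemorrhage (0d, 1D, 3D, 7D) at each time after the onset of disease", and the flow chart in 7.5 schedules repeat CTs.

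For withdrawn cases, Protocol 4.5.3 says that "researchers should actively take measures to complete the final examination as soon as possible to analyze the efficacy and safety". The SAP (section 5, item 3) names a per-protocol set, an FAS and a safety set without defining them, and leaves the handling of deviating cases to a review of trial conduct. SAP section 2 applies LOCF to important data but not to secondary indices.

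**The concern.** Section 2 of the protocol asks whether vitamin K1 prevents an increase in bleeding. Extension into the ventricle, or growth into an irregular shape, is one way in which bleeding increases, and it is also the state described in exclusion 1. If that criterion can be applied to a follow-up CT, a patient can leave the trial because the outcome occurred. The comparison of volumes is then made among patients selected after randomisation for not having bled further in this way.

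If vitamin K1 reduces such growth and rejection is equally likely for growers in both arms, more control patients are removed and the difference shrinks. If it increases growth, the harm shrinks in the same way. If rejection is applied unevenly, the bias can go in either direction. Patients rejected this way may also lose their 1- and 6-month mRS, on which the SAP states its superiority criterion.

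**Working it through.** **Can 4.4(2) operate after randomisation?**

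1. Item 1 of 4.4 carries an enrolment-error limit. Item 2, directly below it, carries none.
2. Section 4.4 is not purely a list of entry errors. Item 3 can arise only after enrolment.
3. Section 4.5.1 item 4 makes the rejection criteria a ground for exit while the trial is running.
4. Eligibility is not confined to baseline elsewhere either. Inclusion item 6 reads "During the hospitalization, no urokinase and other hemostatic drugs were used", which can be judged only after entry.

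The text therefore permits post-randomisation rejection. It does not say that this is intended.

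**Does the trigger overlap the outcome?** Exclusion 1 is a CT finding, and the outcome is CT volume on days 0, 1, 3 and 7. Any of the three later scans could show the exclusion finding in a patient who was eligible on day 0. (The remark in 7.1 item 4 about not repeating the examination is unclear, but section 8 and the flow chart both need follow-up scans.)

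**Do other provisions keep the data?** Section 4.5.3 asks for one final examination, not the remaining scheduled CTs or the later mRS. The FAS has no definition, so the place of rejected patients is open. LOCF keeps the growth only if volume counts as important data and the scan showing the extension is used. If that scan is set aside as unmeasurable, a volume from before the expansion is carried forward.

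**How large could the effect be?** The documents give no sample size, effect size, standard deviation, growth rate or rejection rate, so there is no planned figure to reproduce. All inputs below are assumptions.

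Let p be the share of patients in an arm whose haematoma grows, G the mean growth among them (zero in the rest), and r the share of growers who are rejected and whose volumes are lost.

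- True mean growth: p × G
- Observed mean growth: G × p(1 − r) / (1 − p × r)

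Worked case, p = 0.20 control and 0.10 treated, r = 0.25 in both arms:

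- Control: 0.20 × 0.75 / (1 − 0.05) = 0.158 G
- Treated: 0.10 × 0.75 / (1 − 0.025) = 0.077 G
- Observed difference 0.081 G against a true 0.100 G, so 81% remains.

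Share of the true difference that remains, by growth rates (control/treated):

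| Growers rejected, control / treated | 20%/10% | 30%/20% | 30%/15% |
|---|---|---|---|
| 0 / 0 | 100% | 100% | 100% |
| 25% / 25% | 81% | 85% | 84% |
| 50% / 50% | 58% | 65% | 64% |
| 100% / 100% | 0% | 0% | 0% |
| 50% / 25% | 34% | 19% | 40% |
| 25% / 50% | 105% | 132% | 108% |

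With no true effect (20% or 30% growers in both arms), rejecting half of the treated growers and 0–25% of the control growers creates a false benefit of 0.05 to 0.12 G.

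Uneven rejection cannot be ruled out. The trial is single blind, section 6.1.1 has the investigators giving the drug, and 4.5.1 has the researchers deciding on exit.

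**The case against.** Items 1 and 2 of 4.4 read naturally as a pair: an inclusion criterion failed, or an exclusion criterion met, and discovered after entry. Item 2 is in the past tense, and exclusions 4 (drug history) and 5 (no consent) are facts at entry. Section 4.5.1 item 4 has a purpose without exclusion 1, since 4.4 item 3 already arises after entry. This stands: an entry-only reading is plausible, and the English is rough. It does not remove the problem, because nothing stops a site from reading item 2 literally, and sites may differ.

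A reader might infer that the plan deletes rejected patients' volumes. No passage says so. Section 4.5.3 wants a final examination for efficacy and safety and a case report form for every case, the SAP names an FAS and tabulates ineligible and dropped-out cases, and the CT that reveals the extension is itself an outcome scan that LOCF could carry forward. That is real but partial protection, for the reasons given in the working.

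A reader might also infer that new liver impairment (exclusion 2) would be lost as a safety outcome by the same route. The documents do not support this. A safety set is named, the SAP lists every adverse event, and Protocol 9.7 follows unresolved events until they resolve or stabilise.

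Finally, it is tempting to say that ventricular blood will be scored as no growth or as shrinkage. Section 4.3 says only that such bleeding cannot be measured accurately. The entry-only reading still leaves that gap: these patients stay in, volume remains the outcome, and no rule covers their scans.

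**Conclusion.** The concern holds as a statement of what the text permits. Sections 4.4(2) and 4.5.1(4) together allow a patient to be rejected for ventricular extension or irregular growth after randomisation, and the existing safeguards do not secure the later CT and mRS data. Under either reading, the plan has no rule for volume in such haematomas.

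The size cannot be found from the documents. Under the assumed growth rates it runs from a loss of 15–19% of the difference, if a quarter of growers are rejected in both arms, to complete loss if all are. These figures assume that rejected volumes are lost and that the other patients have no mean growth. A reader might conclude that the effect would be wiped out, or that the bias always runs towards no difference. Neither follows: the first needs every grower to be rejected, and the second needs similar rejection rates in the two arms.

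This should be fixed. It is an ambiguity with a biased reading available, not a stated rule to discard outcome data.

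**What to change.** 1. Reword 4.4(2) along these lines: *met an exclusion criterion at randomisation, judged only on data obtained before randomisation*.
2. State that exit under 4.5.1(4) does not end follow-up or remove data, and reconcile 4.4 with 4.5.1 on this. The change concerns follow-up and analysis only; decisions on study treatment stay with the existing clinical provisions.
3. Define the FAS in the SAP as all randomised patients, including those who develop intraventricular blood or an irregular haematoma.
4. On the CTs already planned, record new intraventricular blood or irregular shape (yes/no) beside the volume from the Duotian formula. Add a supportive yes/no expansion analysis in which new intraventricular blood counts as expansion.

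The cost is some wording, one case report form field and one extra analysis. Volume data will be slightly noisier because haematomas that are harder to measure stay in. In the illustration, keeping every grower (r = 0) restores the full difference, provided their volumes can be measured. Item 4 is there because that proviso may fail.

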4.5 Exit test standard

4.5.1 The researchers decided to quit

1)During the clinical trial, the subjects experienced other complications, complications,

or special physiological changes, and were not allowed to continue the experiment..

2) Serious adverse events and important adverse events, it is not appropriate to continue to accept the test.

3) The subjects had poor compliance.

4) The test process meets the rejection criteria.

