6.1 Experimental medication

6.1.1 Drug delivery

Test drug: vitamin K1 for injection, specification: 10mg each

Contrast drug: normal saline.

All trials were administered by the investigators in a single blind manner,.

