6.1.5 Test cycle

Medication for 2 days + followed up for 6 months.

7 Test procedure and plan

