7.3 Follow-up visit

1 months (+ 3 days) and 6 months (= 3 days) after the onset of intracerebral hemorrhage: the researchers performed a mRS score using telephone follow-up.

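### Investigator-decided exit under Protocol 4.5.1 is handled as leaving the trial, and nothing keeps the scheduled CTs or the 1- and 6-month mRS, so outcomes can be lost in an outcome-related way

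*Protocol*

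**What the plan says.** Protocol 4.5.1 lists grounds on which the investigator may end a patient's participation:

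- Item 1: complications, "or special physiological changes, and were not allowed to continue the experiment".
- Item 2: "Serious adverse events and important adverse events, it is not appropriate to continue to accept the test".
- Item 3: "The subjects had poor compliance", with no threshold.

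Protocol 4.5.3 says what happens next: "In the case of the withdrawal from the trial, the researchers should actively take measures to complete the final examination as soon as possible", for analysis of efficacy and safety. It adds "All trial cases should be completed in the case report form and the reasons for the withdrawal".

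The trial runs far beyond dosing. Section 6.1.5 gives "Medication for 2 days + followed up for 6 months". Section 8 lists hemorrhage volume at days 0, 1, 3 and 7 as the main outcome. At 1 and 6 months after onset, under 7.3, "the researchers performed a mRS score using telephone follow-up". SAP 5(5)1) bases the superiority conclusion on the change in mRS at 6 months.

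On blinding, 6.1.1 says "All trials were administered by the investigators in a single blind manner". On missing values, SAP 2(1) carries the last observation forward for important data and does not do so for secondary indices.

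**The concern.** Stopping a drug and ending outcome collection are different decisions. Here dosing is over after two days, while the exit rule applies throughout a six-month trial. If a site applies 4.5.1 as written, a patient with a complication at week 2 can leave the trial with no 1- or 6-month mRS, although one telephone call would have obtained each.

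The patients concerned are unlikely to be a random subset. Complications are an exit ground in 4.5.1 and an outcome in section 8. The serious-event definition in 9.1 includes disability and prolonged hospitalization, which lie close to the mRS and to length of stay. Exit may also differ by arm, because the investigator decides and the plan does not say that this person is blinded.

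Whatever SAP 2(1) then does with the gap, an outcome that was never collected cannot be recovered. The choice of carry-forward is a separate matter; this point concerns avoidable gaps in the data to which it would be applied.

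**Working it through.** **Step 1: does exit mean stopping drug or leaving the trial?**

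- For drug only: item 2's wording, in this translation, could refer to treatment. Sections 9.1 and 9.3.1 recognise pausing drug or adjusting the dose as responses to an important adverse event.
- For leaving the trial: 4.5 is headed as an exit standard, item 1 speaks of continuing the experiment, and 4.5.3 speaks of withdrawal from the trial with an early final examination. After day 2 there is no drug left to stop. Because 9.3.1 has its own drug-level rule, 4.5.1 reads more naturally as a further step.

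**Step 2: does anything keep the scheduled outcomes after exit?**

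- 4.5.3: one early final examination and case report form completion; no schedule.
- 7.3: calls are timed from onset; exited patients are not mentioned.
- 7.5 flow chart: appears to mark a CT at discharge or death; this is not the day 3 or day 7 volume.
- 9.7: follows unresolved adverse events only.
- SAP 5(3): decides imputation for deviating cases; collects nothing.

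These can yield partial data, but none guarantees the remaining scheduled CT volumes or the 1- and 6-month mRS.

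**Step 3: what one exit can lose.** Inputs: CT at days 0, 1, 3 and 7 (section 8); mRS at months 1 and 6 (7.3).

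| Time of exit | CT volumes at risk | Telephone mRS at risk |
|---|---|---|
| After day 0 CT, before day 1 CT | 3 of 4 | 2 of 2 |
| After day 1 CT, before day 3 | 2 of 4 | 2 of 2 |
| Day 3 to before day 7 | 1 of 4 | 2 of 2 |
| Day 7 to before month 1 | 0 of 4 | 2 of 2 |
| Month 1 to before month 6 | 0 of 4 | 1 of 2 |

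The 6-month mRS is at risk in every row.

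**Step 4: illustration of size.** The documents give no exit or event rates, so all inputs here are assumed. Let g be the exit share in the test arm minus that in the control arm, m = -1 the mean mRS change in other patients in both arms, and x the true mean change in exiting patients.

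- True arm difference: g(x - m).
- If exits are carried forward as change 0, the observed difference is g(0 - m), so the error is -g·x.
- If exits are left missing, the observed difference is 0, so the error is -g(x - m).

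| x | Carried forward, g = 0.05 | Left missing, g = 0.05 | Carried forward, g = 0.10 | Left missing, g = 0.10 |
|---|---|---|---|---|
| -0.5 | +0.025 | -0.025 | +0.05 | -0.05 |
| 0 | 0 | -0.05 | 0 | -0.10 |
| 0.5 | -0.025 | -0.075 | -0.05 | -0.15 |
| 1 | -0.05 | -0.10 | -0.10 | -0.20 |

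Here g = 0.05 is, for example, exit of 10% v 5%, and g = 0.10 is 15% v 5%. All signs reverse if the control arm exits more. The carried-forward columns need an earlier mRS, which the flow chart does not appear to show, and they ignore any value from the early final examination or, for late exits, the 1-month score.

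For volume, if exiting patients grow by v ml after their last CT and others by 0, the absolute error is g·v under either handling. With v = 2, 5 or 10 ml this is 0.1, 0.25 or 0.5 ml at g = 0.05, and 0.2, 0.5 or 1.0 ml at g = 0.10.

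A second assumed case ties exit to growth. Let 30% of patients in each arm grow by 12 ml, so there is no true effect. Let 10% of growers in one arm and 30% in the other exit, with a pre-growth CT carried forward. The false difference is 12 × (0.30 × 0.90 - 0.30 × 0.70) = 12 × 0.06 = 0.72 ml, in a direction set by which arm exits more. Equal exit with no true effect gives no error.

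**The case against.** The strongest reply is that the plan is silent rather than wrong. Section 9.3.1 answers important adverse events with drug-level measures and does not mention leaving the trial. Item 2 is conditional. Section 7.3 makes no exception for exited patients, and 4.5.3 asks for a final examination and completed forms. A reader might infer from 4.5.1 that every exit does lose the 6-month mRS, or that the protocol never separates stopping drug from leaving the trial. The documents support neither: they fail to say what follows exit, and 9.3.1 does recognise drug interruption as a separate step. The supportable claim is that the data can be lost. Reading item 2 as drug only does not remove the problem, because exit remains available for months after dosing ends and sites could apply the text either way.

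Other parts of the reply also narrow the point:

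- Item 3 has little scope during dosing, which is two once-daily in-hospital drips. Later non-compliance may largely mean unanswered calls, which rewording cannot recover.
- Item 1 refers to other complications and section 8 to those after hemorrhage, so in this translation the overlap is possible rather than certain.
- A reader might infer that exit will differ by arm. That is only a possibility. Section 9.3.1 mentions an emergency envelope, if applicable, which suggests that some treating staff may not know the arm.
- The illustrated errors are small and rest wholly on assumed inputs.

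**Conclusion.** The point holds as a cheap improvement. Exit under 4.5.1 items 1 to 3 is handled as withdrawal from the trial, and no section preserves the scheduled outcomes afterwards. One exit can cost the 6-month mRS at any time before month 6, and one to three of four CT volumes if it comes before day 7. The loss can be outcome-related and may be arm-related.

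Its effect on the result is unknown. A reader might take the illustrated figures as an estimate of bias, or conclude that the comparison is tilted towards vitamin K1. Neither follows: without exit rates, neither size nor direction can be derived. In the mRS illustration, errors range from 0 to 0.20 points in absolute size; in the volume illustrations, from 0.1 to 1.0 ml, apart from the zero-error case of equal exit.

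The conclusion rests on reading 4.5.1 as trial exit. If the sponsor meant drug only, the same clarification is still needed. Consent pages are not in the public documents, so any statement there about follow-up after exit cannot be seen.

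**What to change.** Reword Protocol 4.5.1 and 4.5.3 along these lines:

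> An adverse event, complication or poor compliance may stop study drug but does not end follow-up. Unless consent is withdrawn or contact is lost, the remaining scheduled CTs (days 1, 3 and 7) and the 1- and 6-month telephone mRS are still collected.

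Add to SAP 5(3) that such patients stay in the full analysis set as randomised. The protocol wording alone does not settle this, because the SAP decides the analysis sets. Keep the early final examination for patients who withdraw consent to follow-up and agree to that examination.

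The cost is a short protocol and SAP amendment and, for each patient who would otherwise have exited, up to three CTs and two telephone calls. All of these are already in the schedule, so no new visit is needed.

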4.5.2 The subjects pulled out of their own accord

1) The subjects were unwilling or unable to continue clinical trials and asked the researchers for an exit test.

2) The subjects were not explicitly asked to quit the trial, but those who were not receiving the medication and the test were lost.

